2.4 Secondary endpoints

2.4.1 Confirmatory secondary endpoints

Confirmatory secondary endpoints are listed in Section **4.2.2.1** in the protocol.

All confirmatory secondary endpoints are planned to be assessed at week 56 and will be analysed using the same MI approach as used for the primary endpoints and to address the effectiveness estimand. The statistical models for continuous endpoints will be ANCOVA with factors and covariates listed in [Table 2-4](#) with baseline body weight replaced by baseline measurement of endpoint to be analysed. The statistical model for 10% responders will be analysed using logistic regression in the same way as for 5% responders.

Sensitivity analyses will be carried out for all confirmatory secondary endpoints. See [Table 2-6](#) for details on planned analysis methods, multiple imputation approach and sensitivity analyses.

The efficacy estimand will also be assessed for confirmatory secondary endpoints using MMRM as described for the primary endpoints.

2.4.2 Description of the testing procedure to address the effectiveness estimand for primary and confirmatory secondary endpoints

The tests of superiority of liraglutide 3.0 mg to placebo for each of the endpoints are tested in a hierarchical manner in the order in which the endpoints are presented. The two primary endpoints are included in the statistical testing hierarchy below, even though the primary objective will only be met if superiority of liraglutide 3.0 mg vs. placebo is demonstrated for each of the primary endpoints. The test hierarchy is given in [Table 2-6](#). The first endpoints to be tested are all assessing aspects of weight loss (e.g., relative change in body weight, achieving a certain magnitude of weight loss, and change in waist circumference); these endpoints are followed by endpoints assessing change in weight-related comorbidities and/or consequences of excess body weight and 'feeling and function' indicators.

Table 2–6 Hierarchical order and type of statistical model to address the effectiveness estimand for primary and confirmatory secondary endpoints

Test order	Endpoint	Endpoint type	Statistical model	MI approach	Sensitivity analyses #
Primary endpoint					
1	Change in body weight (%) from baseline to week 56	Continuous	ANCOVA	Jump to reference	McEvoy wANCOVA Sacks Tipping point Unadjusted ANCOVA
2	Proportion of subjects losing at least 5% of baseline body weight at week 56	Binary	Logistic Regression	Jump to reference	McEvoy Sacks Tipping point Risk difference
Confirmatory secondary endpoints					
3	Proportion of subjects losing more than 10% of baseline body weight at week 56	Binary	Logistic Regression	Jump to reference	McEvoy Tipping point
4	Change from baseline to week 56 in waist circumference (cm)	Continuous	ANCOVA	Jump to reference	McEvoy wANCOVA Tipping point
5	Change from baseline to week 56 in HbA1c (%)	Continuous	ANCOVA	Jump to reference	McEvoy wANCOVA Tipping point
6	Change from baseline to week 56 in fasting glucose (%)	Continuous	ANCOVA	Jump to reference	McEvoy wANCOVA Tipping point
7	Change from baseline to week 56 in Short Form-36 (SF-36) v2.0 acute physical functioning score	Continuous	ANCOVA	Jump to reference	McEvoy wANCOVA Tipping point
8	Change from baseline to week 56 in impact of Weight on Quality of Life-Lite (IWQoL-Lite for CT), physical function domain (5-itmes) score	Continuous	ANCOVA	Jump to reference	McEvoy wANCOVA Tipping point

Statistical Analysis Plan
Trial ID: NN8022-4272
UTN: U1111-1177-4903
EudraCT No.: 2015-005619-33

~~CONFIDENTIAL~~

Date:	12 October 2018	Novo Nordisk
Version:	1.0	
Status:	Final	
Page:	20 of 28	

MI Multiple Imputation;
See [Table 2-5](#)

2.4.3 Supportive secondary endpoints

2.4.3.1 Efficacy endpoints

Supportive secondary endpoints are listed in Section 4.2.2.2 in the protocol. The questionnaire for Weight related sign and symptom (WRSS) measure will not be validated until after DBL.

Therefore the total score cannot be calculated and the supportive secondary endpoint “Weight related sign and symptom (WRSS) measure, total score” will not be analysed. Instead frequencies for categorical responses will be presented for each item and by visit.

Supportive secondary endpoints will be evaluated to address the effectiveness estimand. These endpoints will be analysed using the same MI approach as used for the primary and confirmatory secondary endpoints.

In exception, the endpoints total daily basal insulin dose (% of pretrial dose in U), total daily basal insulin dose (U/kg) and total daily insulin dose (U/kg) will not be analysed but only summarised in tables. Endpoint at baseline and change of endpoint will be summarised by week and treatment.

The endpoint mean daytime glucose value will be calculated from the 7-point SMPG profile as area under the curve (AUC) divided by length of time-interval. AUC will be calculated using the linear trapezoidal method. Missing points in the 7-point SMPG profile are ignored for the calculation.

The statistical model for continuous endpoints will be ANCOVA with factors and covariates listed in [Table 2–4](#) with baseline body weight replaced by baseline measurement of endpoint to be analysed. The statistical model for proportions will be analysed using logistic regression.

In addition to the supportive secondary efficacy endpoints regarding IWQoL-Lite for CT listed in the protocol, analyses and outputs for the IWQoL-Lite for CT physical domain (not to be confused with IWQoL-Lite for CT physical function domain) will be made.

2.4.3.2 Safety endpoints

Descriptive statistics for all safety endpoints will be provided with the aim to compare liraglutide 3.0 mg and placebo. All analyses and tabulations will be done using the safety analysis set. Unless otherwise stated, no formal statistical analyses are planned for the safety endpoints.

Adverse events and hypoglycaemic episodes will be classified and analysed as ‘in trial’ and ‘on drug’ defined in terms of patient years of observation (PYO) and patient years of exposure (PYE), respectively. For each subject PYO is defined as number of days from date of randomisation until and including date of follow-up visit or date of last contact. For each subject PYE is defined as time intervals of exposure to trial drug including an ascertainment window of 14 days for each exposure interval.

Adverse events

AEs will be coded using the current version of Medical Dictionary for Regulatory Activities (MedDRA). All AEs will be presented based on system organ class, high level group term and preferred terms.

AEs, which occurred while the subject was in trial or on drug will be summarised descriptively, whereas AEs, which occurred before first exposure to trial drug or after the follow-up visit will only be presented in listings. AEs will be displayed in terms of the number of subjects with at least one event (N), the percentage of subjects with at least one event (%), the number of events (E) and the event rate per 100 years (R). Furthermore, AEs will be summarised by seriousness, severity, relation to trial drug, premature treatment discontinuation due to AE and outcome.

Summary tables by system organ class, high level group term and preferred term will be made for all AEs, SAEs, AEs possibly or probably related to trial drug, severe AEs, AEs occurring in at least 5% of the subjects in any arm, and AEs occurring in at least 1% of the subjects in any treatment arm.

AEs requiring completion of specific event forms will be presented in tables and listings. In addition, time to occurrence of these AEs will be presented in cumulative incidence plots.

Hypoglycaemic episodes

All hypoglycaemic episodes will be summarised in terms of N, %, E, rate as on drug (PYE) and in trial (PYO) and using same ascertainment window of 14 days as for AEs.

In addition to summary tables for hypoglycaemic episodes, an analysis and outputs for number of hypoglycaemic episodes will be made. The number of hypoglycaemic episodes occurring on-drug after 56 weeks of treatment will be analysed using a negative binomial regression model with a log-link function and the logarithm of the on drug time period as offset. The model will include treatment, sex, BMI group and sulphonylurea (Yes, No) as fixed factors and baseline body weight in kg and HbA1c in % as covariates.”

Classification of Hypoglycaemia:

Treatment emergent: hypoglycaemic episodes will be defined as treatment emergent if the onset of the episode occurs during on drug time intervals.

Nocturnal hypoglycaemic episodes: are episodes occurring between 00:01 and 05.59 both inclusive.

Hypoglycaemic episodes are classified according to the Novo Nordisk classification of hypoglycaemia (see [Figure 2-2](#)) and the ADA classification of hypoglycaemia (see [Figure 2-3](#)).

Novo Nordisk classification of hypoglycaemia

In normal physiology, symptoms of hypoglycaemia occur below a plasma glucose level of 3.1 mmol/L (56 mg/dL)²⁰ Therefore, Novo Nordisk has included hypoglycaemia with plasma glucose levels below this cut-off point in the definition of blood glucose (BG) confirmed hypoglycaemia.

Novo Nordisk uses the following classification (see **Figure 2–2 Novo Nordisk classification of hypoglycaemia**Figure 2–2) in addition to the ADA classification:

Severe hypoglycaemia according to the ADA classification¹¹.

[figure not shown]
Symptomatic BG confirmed hypoglycaemia: An episode that is BG confirmed by plasma glucose value <3.1 mmol/L (56 mg/dL) **with** symptoms consistent with hypoglycaemia.

Asymptomatic BG confirmed hypoglycaemia: An episode that is BG confirmed by plasma glucose value <3.1 mmol/L (56 mg/dL) **without** symptoms consistent with hypoglycaemia.

Severe or BG confirmed symptomatic hypoglycaemia: An episode that is severe according to the ADA classification¹¹ or BG confirmed by a plasma glucose value <3.1 mmol/L (56 mg/dL) **with** symptoms consistent with hypoglycaemia.

BG confirmed hypoglycaemia: An episode that is BG confirmed by a plasma glucose value <3.1 mmol/L (56 mg/dL) **with** or **without** symptoms consistent with hypoglycaemia.

Severe or BG confirmed hypoglycaemia: An episode that is severe according to the ADA classification¹¹ or BG confirmed by a plasma glucose value <3.1 mmol/L (56 mg/dL) **with** or **without** symptoms consistent with hypoglycaemia.

Note: Glucose measurements are performed with capillary blood calibrated to plasma equivalent glucose values

Figure 2–2 Novo Nordisk classification of hypoglycaemia

ADA classification¹¹ of hypoglycaemia

[figure not shown]
Severe hypoglycaemia: An episode requiring assistance of another person to actively administer carbohydrate, glucagon, or take other corrective actions. Plasma glucose concentrations may not be available during an event, but neurological recovery following the return of plasma glucose to normal is considered sufficient evidence that the event was induced by a low plasma glucose concentration.

Asymptomatic hypoglycaemia: An episode not accompanied by typical symptoms of hypoglycaemia, but with a measured plasma glucose concentration ≤ 3.9 mmol/L (70 mg/dL).

Documented symptomatic hypoglycaemia: An episode during which typical symptoms of hypoglycaemia are accompanied by a measured plasma glucose concentration ≤ 3.9 mmol/L (70 mg/dL).

Pseudo-hypoglycaemia: An episode during which the person with diabetes reports any of the typical symptoms of hypoglycaemia with a measured plasma glucose concentration > 3.9 mmol/L (70 mg/dL) but approaching that level.

Probable symptomatic hypoglycaemia: An episode during which symptoms of hypoglycaemia are not accompanied by a plasma glucose determination but that was presumably caused by a plasma glucose concentration ≤ 3.9 mmol/L (70 mg/dL).

Note: Glucose measurements are performed with capillary blood calibrated to plasma equivalent glucose values

Figure 2–3 ADA classification of hypoglycaemia

Physical examination

Outcome of the physical examination at screening and change in the physical examination category at week 56 will be summarised in tables.

Pulse

Pulse (beats/min) at baseline and change of pulse at week 56 will be summarised in tables by week and treatment. Categories based on the maximum change from baseline until week 56 (>0 , >5 , >10 , >20 beats/min) and categories based on the maximum value until week 56 (>80 , >90 , >100 beats/min) will be included in summary tables. Additionally, change in pulse from baseline to week 56 will be evaluated in the in trial observation period similar as in the primary analysis for the primary estimand but using the safety analysis.

ECG

Shifts in the ECG category from screening to week 56 will be summarised in tables.

Laboratory measurements

Laboratory values below the lower limit of quantification (LLOQ) will be set to $\frac{1}{2}$ LLOQ.

Laboratory safety parameters are measured throughout the trial and comprise haematology and biochemistry as defined in the flow chart.

The distribution of each continuous laboratory parameter will be presented using box plots by treatment and week. Continuous laboratory parameters will be compared to the relevant reference ranges and results will be presented.

Amylase and lipase

Shifts from baseline to highest value in trial period to UNL, 2xUNL and 3xUNL will be summarised in tables.

Mean plots, geometric mean plots and box plots by gender, visit and treatment will be prepared. Change from week 0 to week 56 will also be presented by empirical distribution plots.

Number and percentage of subjects with amylase and lipase levels \geq UNL, \geq 2xUNL or \geq 3xUNL will be tabulated by week and treatment. Subjects with values \geq 2xUNL will additionally be presented with spaghetti plots.

Additionally, change in amylase and lipase from baseline to week 56 will be evaluated in the in trial observation period similar to the primary analysis for the primary estimand but using the safety analysis set.

Calcitonin

Number, percentage and incidence of subjects with persistent (all post-baseline measurements) and incidental (at least one post-baseline measurement) increases in calcitonin for the criteria below will be tabulated for all subjects, males and females.

From baseline <UNL to \geq UNL

From baseline <UNL to \geq 20 ng/L

From baseline <UNL to \geq 50 ng/L

From baseline <20 ng/L to \geq 20 ng/L

From baseline <50 ng/L to \geq 50 ng/L

Number and percentage of subjects with calcitonin levels \geq UNL, \geq 1.5xUNL or \geq 20 ng/L and \geq 50 ng/L will be tabulated by visit and treatment.

A summary table showing number and percentage of observations < and \geq LLOQ, minimum, Q25, median, Q75, maximum and geometric mean will be prepared by gender, visit and treatment.

The distribution of the calcitonin values across treatment group and time will be shown in plots by gender and total actual levels. Geometric means will be plotted by visit and treatment in order to assess the pattern of the longitudinal changes.

In addition, a scatter plot of baseline vs. maximum post-baseline calcitonin value will be prepared.

Longitudinal changes with calcitonin \geq 20ng/L will be evaluated with spaghetti plots.

Subjects with at least one post-baseline calcitonin value above 20 ng/L will be listed.

The listings will include treatment, age, gender, smoking habits at baseline, risk factor information (use of relevant concomitant medication at time of assessment [proton pump inhibitors and H2 blockers] and medical history of thyroid disorder) and calcitonin values.

3 Changes to the statistical analyses planned in the protocol

3.1 Deviation from analyses as described in the protocol

- Factors and covariates to be included in the statistical modelling of the efficacy related endpoints has been reduced to only include treatment, gender and BMI group as factors and

baseline body weight in kg as a covariate to align with the current modelling strategy in obesity projects at Novo Nordisk A/S.

The following table (**Table 2–4** in the protocol):

Factors and covariates at baseline	Type	Categories
Randomised treatment	Factor	Liraglutide 3.0 mg, placebo
Sulphonylurea	Factor	Yes, no
Body weight (kg)	Covariate	Not applicable
BMI (kg/m ²)	Factor	[27,30[, [30,35[, [35,40[, ≥40
Gender	Factor	Male, female
Insulin type	Factor	Insulin detemir, other basal insulin
Insulin dose	Covariate	Not applicable
HbA1c	Factor	≤ 8.0%, > 8.0%

has been replaced by:

Factors and covariates at baseline	Type	Categories
Randomised treatment	Factor	Liraglutide 3.0 mg, placebo
Body weight (kg)	Covariate	Not applicable
BMI (kg/m ²)	Factor	[27,30[, [30,35[, [35,40[, ≥40
Gender	Factor	Male, female

- A MMRM is used for the efficacy estimand and only assessments from subjects who are taking the randomised treatment until end of trial or until first discontinuing of trial drug (either temporarily or permanent) are included. In the protocol, a trial drug pause of more than two days is defined as a treatment discontinuation, but a treatment discontinuation should have been defined as a trial drug pause of more than 7 days, which is also the information collected in the eCRF.

The following text:

”A pause of less than three consecutive days is not regarded as discontinuation for this analysis.”

has been replaced by:

”A pause of less than eight consecutive days is not regarded as discontinuation for this analysis.”

- Since subgroup analyses are only planned to be done for factors and covariates included in the statistical modelling of efficacy related endpoints, a subgroup analysis for baseline insulin dose is no longer required as per protocol.

The following text:

“For baseline weight and insulin dose, categories based on quartiles will be used.”

has been replaced by:

“For baseline weight, categories based on quartiles will be used.”

- The WRSS questionnaire will not be validated until after DBL. Therefore the total score cannot be calculated and the supportive secondary endpoint “Weight related sign and symptom (WRSS) measure, total score” cannot be analysed.

The following text has been added:

“The questionnaire for Weight related sign and symptom (WRSS) measure will not be validated until after DBL. Therefore the total score cannot be calculated and the supportive secondary endpoint “Weight related sign and symptom (WRSS) measure, total score” will not be analysed. Instead frequencies for categorical responses will be presented for each item and by visit.”

- The following three supportive secondary efficacy endpoint Total daily basal insulin dose (% of pre-trial dose in U), Total daily basal insulin dose (U/kg) and Total daily insulin dose (U/kg) will not be analysed but only summarised in tables, as no additional relevant information will be gained from analysing four endpoints all concerning change in insulin dose from baseline to week 56

The following text has been added:

“In exception, the endpoints total daily basal insulin dose (% of pretrial dose in U), total daily basal insulin dose (U/kg) and total daily insulin dose (U/kg) will not be analysed but only summarised in tables. Endpoint at baseline and change of endpoint will be summarised by week and treatment.”

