17.3.1.1 Statistical model for the primary endpoint % weight change

The primary endpoint % weight change will be analysed using analysis of covariance (ANCOVA) including the factors and covariates listed in [Table 17–4](#).

Table 17–4 Factors and covariates for the analysis of the primary endpoints

Factors and covariates at baseline	Type	Categories
Randomised treatment	Factor	Liraglutide 3.0 mg, placebo
Sulphonylurea	Factor	Yes, no
Body weight (kg)	Covariate	Not applicable
BMI (kg/m ²)	Factor	[27,30[, [30,35[, [35,40[, ≥40
Gender	Factor	Male, female
Insulin type	Factor	Insulin detemir, other basal insulin
Insulin dose	Covariate	Not applicable
HbA1c	Factor	≤ 8.0%, > 8.0%

The factors and covariates will be included in the model as main effects in an additive structure. The estimated treatment difference between liraglutide 3.0 mg and placebo will be reported together with the associated two-sided 95% CI and corresponding p-value.

The superiority test of liraglutide 3.0 mg vs. placebo will be carried out as follows:

Let $\mu_{\text{liraglutide}}$ and μ_{placebo} denote the true mean of % weight change for liraglutide 3.0 mg and placebo group, respectively. The hypothesis and the alternative are

H: $\mu_{\text{liraglutide}} \geq \mu_{\text{placebo}}$ against the alternative $H_A: \mu_{\text{liraglutide}} < \mu_{\text{placebo}}$.

The hypothesis will be rejected and superiority claimed, if the upper limit of the estimated two-sided 95% CI is below 0.

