17.3.4 Subgroup analyses for primary endpoints

For the effectiveness estimand, subgroup analyses will be done for the factors listed and categorised as in [Table 17-4](#). For baseline weight and insulin dose, categories based on quartiles will be used. The subgroup analyses will be done separately for each of these by including interaction term(s) with randomised treatment arm in the respective models (ANCOVA or logistic regression).

Figure 17–1 Illustration of imputation approaches

[figure not shown]

Table 17–5 Overview of handling of missing values

Approach	Description	Assumptions
Jump to reference (multiple imputation)	Liraglutide and placebo MT+MD imputed from placebo AT+AD (i.e., all available placebo assessments at week 56)	- Liraglutide MD lose any treatment effect instantly after drop-out - Placebo AT and placebo AD are assumed to have same weight loss
McEvoy (multiple imputation)	Separately for the two randomised treatment arms: MD imputed from AD by matching on time (month) of drop-out MT imputed from AT	- AD is representative of the MD for each randomised treatment arm - AT is representative of the MT for each randomised treatment arm
Weighted ANCOVA (wANCOVA)	No imputation. Separately for the two randomised treatment arms: AD subjects are up-weighted relative to their proportion of AD+MD and timing of drop-out AT subjects are up-weighted relative to their proportion of AT+MT	- AD is representative of the MD for each randomised treatment arm - AT is representative of the MT for each randomised treatment arm
Sacks (single imputation)	Liraglutide MD imputed by minimum of LAO+0.3 kg and baseline value for each month from drop-out to week 56 and either a) Placebo MD imputed by minimum of LAO+0.3 kg and baseline value for each month from drop-out to week 56 or b) MT (both randomised treatment arms) and placebo MD are imputed by LAO	a) Liraglutide and placebo MD lose any treatment effect linearly after drop-out. b) Only liraglutide MD lose any treatment effect linearly after drop-out. No change in treatment effect since LAO for others.
Tipping point (single imputation)	Liraglutide MD imputed by minimum of LAO+X kg (X in steps of 0.1) and baseline value for each month from drop-out to week 56. MT (both randomised treatment arms) and placebo MD are imputed by LAO	Only liraglutide MD lose any treatment effect linearly after drop-out. No change in treatment effect since LAO for others

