2.1 Sample size calculation

The sample size calculation is based on the analysis approach addressing the primary estimand for the primary endpoints change in body weight (%) from baseline to week 56 (% weight change) and proportion of subjects losing $\geq 5\%$ of baseline body weight at week 56 (5% responders).

The two primary endpoints and all confirmatory secondary endpoints will be tested in a hierarchical order.

The study design is a 1:1 randomisation, stratified by sulphonylurea (yes/no) with 400 subjects in total (200 subjects in each arm). The sample size calculation does not take stratification into account. Please see [Table 2–2](#) for general specifications on sample size and power calculation.

Table 2–2 General specifications for sample size and power calculation

Endpoint	Statistical test	Minimum required power (%)
% weight change	Two-group Satterthwaite unpooled t test on the mean difference with $\alpha=0.05$ assuming unequal variances	90.0 (marginal)
5% responders	Pearson chi-square test for two independent proportions with $\alpha=0.05$	90.0 (marginal)

α : two-sided significance level

In the following paragraphs treatment differences and standard deviations (SD) are given without units.

Body weight measurements from returning discontinuing subjects will be used in the primary analysis. But for the sample size calculations, it is assumed that all subjects who discontinue will not return at week 56 and assume that they have a % weight change like placebo subjects who completed the trial. It is expected that % weight change for liraglutide 3.0 mg subjects who discontinue might be somewhere in between completing placebo subjects and completing liraglutide 3.0 mg subjects. The assumption is thus expected to lead to a conservative effect estimate. A 30% discontinuation is assumed based on findings in trial NN8022-1922.

Based on findings from NN8022-1922, a difference in % weight change between liraglutide 3.0 mg and placebo of -4 (-6% vs. -2% , $SD=6$) is assumed among completing subjects. Adjusting for 30% discontinuation and using a mixture distribution, a difference of -2.8 is expected in the primary analysis. A sample size of 400 subjects (200 in each arm), gives a marginal power of 99.5%.

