2.3.1.1 Statistical model for the primary endpoint % weight change

The primary endpoint % weight change will be analysed using analysis of covariance (ANCOVA) including the factors and covariates listed in [Table 2-4](#).

Table 2-4 Factors and covariates for the analysis of the primary endpoints

Factors and covariates at baseline	Type	Categories
Randomised treatment	Factor	Liraglutide 3.0 mg, placebo
Body weight (kg)	Covariate	Not applicable
BMI (kg/m ²)	Factor	[27,30[, [30,35[, [35,40[, ≥40
Gender	Factor	Male, female

The factors and covariates will be included in the model as main effects in an additive structure. The estimated treatment difference between liraglutide 3.0 mg and placebo will be reported together with the associated two-sided 95% CI and corresponding p-value.

The superiority test of liraglutide 3.0 mg vs. placebo will be carried out as follows:

Let $\mu_{\text{liraglutide}}$ and μ_{placebo} denote the true mean of % weight change for liraglutide 3.0 mg and placebo group, respectively. The hypothesis and the alternative are

H: $\mu_{\text{liraglutide}} \geq \mu_{\text{placebo}}$ against the alternative H_A : $\mu_{\text{liraglutide}} < \mu_{\text{placebo}}$.

The hypothesis will be rejected and superiority claimed, if the upper limit of the estimated two-sided 95% CI is below 0.

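### The SAP drops sulphonylurea, the trial's only stratification factor, from Table 2-4 and so from every confirmatory model; restoring it is a small, nearly free improvement

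*SAP*

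**What the plan says.** SAP 2.1 describes a "1:1 randomisation, stratified by sulphonylurea (yes/no) with 400 subjects in total". No other stratification factor is named. Protocol 17.3.1.1, Table 17-4 ("Factors and covariates for the analysis of the primary endpoints"), includes sulphonylurea yes/no.

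SAP 3.1 states that the covariate set "has been reduced to only include treatment, gender and BMI group as factors and" baseline body weight as covariate, "to align with the current modelling strategy in obesity projects at" the sponsor. Sulphonylurea, insulin type, insulin dose and HbA1c group are all removed.

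SAP 2.3.1.1 says that % weight change "will be analysed using analysis of covariance (ANCOVA) including the factors and covariates listed in" Table 2-4. The same table is called by:

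- the 5% responder logistic model (2.3.1.2)
- imputation step 1 (2.3.2.2)
- the MMRM (2.3.3)
- the subgroup list (2.3.4)
- the confirmatory secondary models (2.4.1)
- the supportive secondary ANCOVAs (2.4.3.1)

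The SAP keeps sulphonylurea in three places: the efficacy-estimand responder model (2.3.3), the hypoglycaemia model (2.4.3.2), and one added sensitivity analysis of the primary endpoints (2.3.2.2), whose imputation step is left as in the primary approach.

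On subgroups, protocol 17.3.4 says "subgroup analyses will be done for the factors listed and categorised as in" Table 17-4, which includes sulphonylurea. SAP 3.1 notes only that "a subgroup analysis for baseline insulin dose is no longer required as per protocol".

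**The concern.** A trial that balances its arms on a factor would normally analyse by that factor. If sulphonylurea use predicts outcome beyond baseline weight, BMI group and gender, a model that omits it leaves its variance in the residual although the design has already removed it from the treatment comparison. The reported standard error is then too wide and the test slightly conservative. In the logistic model the odds ratio also moves a little towards 1.

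The stated reason does not address how this trial randomises, and the omission is not applied consistently. The efficacy-estimand responder model adjusts for sulphonylurea, but the MMRM that supplies its classifications does not. A planned subgroup analysis is also lost without being named in the list of changes.

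**Working it through.** **Inputs from SAP 2.1.** 200 subjects per arm, two-sided 5%; expected difference in % weight change −2.8, SD 6.3 and 6.0; 5% responders 49% vs 31%; 30% discontinuation.

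**Assumptions not in the documents.** Share of sulphonylurea users p = 30% (range 20 to 50%); user/non-user difference d = 1, 2 or 3 points in % weight change beyond the retained covariates; within-stratum SD 6.

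**1. The plan's own power.** 0.7 × (−6) + 0.3 × (−2) = −4.8, and SD = √(36 + 0.21 × 16) = 6.27. The Satterthwaite t test gives 99.5%, as stated. For responders a normal approximation gives 95.9% against the stated 95.7%. The product 0.995 × 0.957 = 95.2% also agrees.

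**2. ANCOVA, complete data.** R² = p(1−p)d² / (36 + p(1−p)d²); SE excess = 1/√(1−R²) − 1; true size = 2[1 − Φ(1.96/√(1−R²))]. For d = 3: p(1−p)d² = 0.21 × 9 = 1.89, R² = 1.89/37.89 = 0.050, SE excess = √(37.89/36) − 1 = 2.6%.

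For power, the within-stratum SE is √((6.3² + 6.0²)/200) = 0.615. With the factor, power is Φ(2.8/0.615 − 1.96) = 99.52%. Without it, power is Φ((2.8 − 1.96 × SEm)/0.615), where SEm adds p(1−p)d² to each arm's variance (0.630 at d = 3).

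| d | SE too wide by | True size | Power without factor | Loss (points) |
|---|---|---|---|---|
| 1 | 0.3% | 4.9% | 99.51% | 0.01 |
| 2 | 1.2% | 4.7% | 99.49% | 0.03 |
| 3 | 2.6% | 4.4% | 99.45% | 0.07 |

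With 20% to 50% users, the 3-point SE excess is 2.0% to 3.1%.

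**3. Logistic, complete data.** Simulation with 60 users and 140 non-users per arm, 400,000 trials per scenario. With the factor omitted at d = 3, the mean model SE against the sampling SD of the log odds ratio is 0.2171/0.2149 (31% vs 31%), 0.2005/0.1980 (49% vs 49%) and 0.2090/0.2068 (49% vs 31%), an excess of about 1%. Null size at d = 3 is 4.57% and 4.75% without the factor, 4.96% and 4.84% with it. Power without/with the factor at d = 1, 2, 3 is 95.79/95.84, 95.88/96.07 and 96.01/96.42%. The odds ratio is 2.15 without the factor and 2.16, 2.17 and 2.20 with it.

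**4. Jump to reference with Rubin pooling, d = 3.** 4,000 trials per scenario, 50 imputations, data missing completely at random and equally by arm. SEs are at a −4 difference among observed subjects. The middle SE column mimics the added sensitivity analysis, but with sulphonylurea alone added. The recovered share is the part of the SE gap that this version closes, computed from unrounded SEs.

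| Missing | SE, factor in neither step | Analysis step only | Both steps | Recovered | Null rejection, neither | Both |
|---|---|---|---|---|---|---|
| 5% | 0.634 | 0.621 | 0.619 | 87% | 3.5% | 3.8% |
| 10% | 0.653 | 0.641 | 0.637 | 75% | 2.6% | 2.9% |
| 20% | 0.686 | 0.677 | 0.670 | 53% | 1.3% | 1.8% |
| 30% | 0.716 | 0.710 | 0.699 | 38% | 0.7% | 0.9% |

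The planned procedure is already below 5% either way, so the gain is a slightly smaller SE (0.716/0.699, or 2.4%, at 30% missing). The 30% row is the plan's planning device ("But for the sample size calculations, it is assumed that all subjects who discontinue will not return at week 56"), not an expected missing rate.

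**5. Confirmatory secondaries, complete data.** At R² of 0.6, 2.3 and 5%, with the plan's differences and SDs, marginal power losses are 0.1, 0.3 and 0.7 points for waist and 0.2, 0.9 and 2.0 points for IWQoL physical function. Multiplied by the plan's effective power of the preceding endpoints (84.7% and 16.0%), they become 0.1, 0.3, 0.6 and 0.04, 0.1, 0.3 points. The largest is SF-36 physical functioning: at R² 5%, 19.9% without the factor against 21.4% with it, so 1.5 × 0.781 = 1.2 points.

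**The case against.** The strongest reply is that there is no demonstrated harm. The current analysis is valid, the change is disclosed, and the SAP adds a sensitivity model with every removed covariate. The documents give neither the share of users nor any effect of sulphonylurea on weight. Protocol 5.2 ties the stratification to hypoglycaemia, and the hypoglycaemia model keeps the factor. All of that is right and keeps the point minor. It does not supply a trial-specific reason for the omission. The sensitivity model covers only the primary endpoints and leaves the factor out of its imputation step. Protocol 5.2 also links glycaemic control to body weight through insulin dose, so a prognostic effect is plausible.

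Four narrower points stand:

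- SAP 3.1 states a general rule that subgroups follow the model factors, so the loss of the sulphonylurea subgroup can be inferred. It is still not named, and the insulin type and HbA1c subgroups go the same way.
- The MMRM nests its terms within visit, so restoring the factor there adds up to 22 terms (visits 3 to 24), not one.
- The shift in the odds ratio is non-collapsibility, a different conditional quantity, not an error.
- The complete-data calculations borrow differences and SDs already adjusted for 30% discontinuation. The primary calculation treats the SDs as within-stratum and the secondary calculation treats them as marginal. The effect of this is trivial.

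**Conclusion.** The point holds and is minor. One deleted row takes the only stratification factor out of every confirmatory model, for a reason unrelated to this trial's design. Over the assumed range the cost is an ANCOVA standard error up to about 3% too wide, at most 0.07 points of power for weight change, 0.4 points for 5% responders and about 1.2 points of effective power for the weakest secondary endpoint.

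Type I error was not inflated in any scenario computed, no claim is made about the MMRM's test size, and no conclusion is expected to change. These sizes depend on an assumed share of users and an assumed prognostic effect. The omission itself and the unnamed loss of the subgroup analysis do not depend on any assumption.

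**What to change.** Before database lock, which SAP 2.4.3.1 treats as still to come, restore the row for sulphonylurea (factor; yes, no) in SAP Table 2-4 and in the replacement table in 3.1. Add sulphonylurea to the sentence in 3.1 that lists the retained factors. The primary models, imputation step 1, the MMRM, the confirmatory and supportive secondary models and the subgroup list then pick it up by reference. The imputation sentence of the added sensitivity analysis needs no edit. The exploratory weight analyses in 2.3.5 list their own covariates, so the table change does not reach them. SAP 3.1 should also name the insulin type and HbA1c subgroups as dropped if they remain so.

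The cost is SAP wording, one degree of freedom in each ANCOVA and logistic model, up to 22 visit-specific terms in the MMRM (tolerable with 400 subjects), and a subgroup output for each primary endpoint that the protocol had already planned. No new data are needed. In the retrieved drop-out imputation, fitted by arm and month, the SAP's existing fallback to coarser timing covers the extra covariate. After lock and unblinding the primary model should not be changed, and the added sensitivity analysis should carry the point.
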